## 5 Statistical analyses

### 5.1 General considerations

This SAP will address the details of the descriptive statistics implemented on all arms (1, 2, 3 and 4) at the 56-week cut-off of trial NN7415-4311. The 56-week cut-off is defined as when all patients in arms 2, 3 and 4 have completed visit 13a (or permanently discontinued treatment). After the last patient has been randomised, any patient that due to the COVID-19 pandemic is prevented from restarting the new dosing regimen will no longer be used to determine the 56-week cut-off.

Unless specified otherwise, the endpoints/assessments will be presented using the analysis sets as displayed in [Table 1](#).

**Table 1 Analysis sets used for analyses and/or presentations of endpoints/assessments**

Endpoint/assessment categories a	Subject Analysis Set	Analysis Data Sets
Bleeding episodes	FAS	On-treatment without ancillary therapy excl. data on initial regimen for subjects exposed to both regimens
PK, PD and safety not relating to events	SAS	On-treatment without data on initial regimen
Safety relating to events b	SAS	On-treatment and On-treatment without data on initial regimen

aWhich endpoints/assessments that belong under each category can be found in section 9 of the protocol version 7.

bThis specifically refers to: number of thromboembolic events, number of hypersensitivity type reactions, number of injection site reactions, number of patients with antibodies to concizumab, and number of adverse events.

For arms 2-4 the target joints registered at baseline will be used for the assessment done at week 56. For arm 1 the target joint evaluation done at visit V9a will be used for assessment at week 56.

Continuous endpoints/assessments will be presented using descriptive statistics which will include min, max, mean, SD, median, and quartiles. For PK endpoints/assessments, the descriptive statistics will also include geometric mean and geometric CV. Event data (including AEs) will be summarised including number of subjects with an event/episode, percentage of subjects with an event/episode, number of events/episodes and rate of events/episodes. Categorical assessments will be summarised by number and percent of subjects in each category. Presentations of results will be by arm and visit (when applicable) and when relevant arm 1 will be split into two parts with on-demand treatment and concizumab treatment.

Baseline for the assessments done at week 56 is defined as the latest non-missing measurement recorded before the time of the first administration of concizumab with the new dosing regimen (arms 2-4 and arm 1 after receiving concizumab) or recorded before randomisation to the on-demand administration (arm 1). If this measurement is missing for arms 2-4 or a subject from arms 2-4 chooses not to restart on concizumab, then the baseline obtained prior to the initial dosing regimen will be used (if available). If the V9a measurement is missing for arm 1 concizumab part,

the latest measurement recorded prior to V9a will be used as a concizumab baseline for arm 1 subjects.

As described in the protocol, if a patient withdraws from trial prior to visit 9/9a/10a (last treatment visit in the main part of the trial), the investigator should ask the patient if he is willing, as soon as possible, to have assessment performed according to visit 9/9a/10a. If the patient withdraws from trial after visit 9a/10a, he should have assessment performed according to visit 26a (last treatment visit in the extension part of the trial). Any values obtained because of this are in scope for being reallocated to a (planned) scheduled visit. Only the value(s) that fulfil the below reallocation rules can be used in summaries and the analyses. The value(s) will be reallocated to a (planned) scheduled visit if the following apply:

- The visit falls within an extended visit window of +/- 7 days of the (planned) scheduled visit.
- The same parameter was planned for assessment but was not assessed at the scheduled visit.
- The scheduled visit is neither a screening visit (visit 1/1a), a randomisation visit (visit 2/2a) or a V9/V9a (only relevant if the patient withdraws from the trial after V9a/10a).

In terms of bleed related endpoints, the bleed rate is defined as the number of bleeds over the respective observation periods. Multiple bleeding locations at the same time point will be counted as one bleeding episode. As a general rule, a treated bleed is defined as any bleed where the use of a factor-containing product is reported between the start and stop time of a bleed. Further, the endpoints will not include re-bleeds. A re-bleed is defined as a bleeding episode (worsening of bleeding site conditions e.g. swelling, pain) starting within 72 hours after stopping treatment of a previous treated bleeding episode (or re-bleed) at the same anatomical location. Note that there can be more than one re-bleed related to the same bleed. If a bleeding episode occurs in the same location more than 72 hours after stopping treatment of a previous bleeding episode (or re-bleed) in the same location, the bleed is defined as a new bleeding episode.

Pharmacokinetic concentration values below lower limit of quantification (LLOQ) is handled as described below:

Timing of values below LLOQ	Imputation	Use of imputed values
Values below LLOQ obtained before time of the first administration with the initial dosing regimen and with the new dosing regimen	Set to 0 (zero)	Plots and derivation of AUC
All other values below LLOQ	Set to LLOQ/2	Plots and derivation of AUC

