| c) Visit will take place after the concizumab exposure levels are available according to in Section 9.2.2                                                                                                                             |
| d) Only patients enrolled after the treatment pause will sign the Informed Consent at visit 1a                                                                                                                                                        |
| e) Only patients enrolled in the trial before the treatment pause and allocated to arm 2, 3 and 4, will re-consent at Visit 2a                                                                                                                        |
| f) Only patients enrolled in the trial before the treatment pause and randomised to arm 1, will re-consent at visit 9a                                                                                                                                |
| g) Only applicable for arm 1 patients, who are receiving concizumab at Visit 9a                                                                                                                                                                       |
| h) Only applicable for patients in arm 2, 3 and 4, who are receiving concizumab at visit 2a                                                                                                                                                           |
| i) Only applicable for patients enrolled in the trial before treatment pause. Site must ensure patients do not violate discontinuation criteria according to Section 8.1 before reinitiating dosing with concizumab                   |
| j) Patients randomised to arm 2 before the treatment pause will not be re-randomised at visit 2a                                                                                                                                                      |
| k) Weight only, except at visit 1 where height is measured                                                                                                                                                                                            |
| l) For patients having concizumab dosing at visit 2a there will be a 24-hour PK session at visit 2a and 9a. Please see details for PK sampling in Section 2.1 . For on-demand patients (arm 1) only the pre-dose sample will be taken |

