#### Patients who were enrolled before the pause

Patients who were randomised or allocated to treatment in this trial before the pause, should re-enter the trial as outlined in [Table 1](#)

**Table 1** Visit overview for patients restarting this trial

| Allocation before the pause | Allocation at restart |
|-----------------------------|-----------------------|
| Arm 1                       | Arm 1 - visit 9a      |
| Arm 2                       | Arm 2 - visit 2a      |
| Arm 3                       | Arm 3 - visit 2a      |
| Arm 4                       | Arm 4 - visit 2a      |

Note: Visit 9a is the first visit in the extension part for arm 1. At visit 9a, the patients in arm 1 will start concizumab PPX.

[Table 2](#) below summarises the expected numbers of randomised/enrolled patients in each arm. In total 136 patients are expected to be enrolled; this includes patients enrolled before as well as after the pause. The aim is to have approximately 15 unique HAwI and HBwI adolescent patients defined as patients between  $\geq 12$  to  $< 18$  years at trial start.

**Table 2** Randomisation/enrolment overview

[figure not shown]
|      | Number of patients randomised/enrolled |       |          |                             |
|------|----------------------------------------|-------|----------|-----------------------------|
|      | Arm 1                                  | Arm 2 | Arm 3    | Arm 4
(PPX or on-demand) |
| HAwI | 9                                      | 18    | Up to 15 | 60                          |
| HBwI | 8                                      | 16    | Up to 10 |                             |

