### **9.1.4 Target Joints**

All current target joints, including number of bleedings during the last 12 months, must be registered. A target joint is defined as three or more spontaneous bleeds into a single joint within a consecutive 6-month period. Where there have been  $\leq 2$  bleeds into the joint within a consecutive 12-month period the joint is no longer considered a target joint. Surgical joint bleeds should not be included in the target joint count.

Following information will be collected in the eCRF:

- Location
- Position (left/right)
- Number of bleeding episodes the last 12 months

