## **5.5 Exploratory efficacy endpoints analysis**

### **5.5.1 Bleed-related assessments**

The assessments related to bleeding episodes are defined in section [6.2](#).

The definition of bleeding rate, treated bleeds and re-bleeds are defined in the section [5.1](#) of this document and in section 10.3 of protocol version 7. The definition of a target joint is given in the protocol section 9.1.4.

ABR will be calculated at an individual basis as

$$ABR = \left( \frac{\text{Number of treated spontaneous or traumatic bleeds}}{\text{Number of days in the analysis data set}} \right) \times 365.25$$

The continuous/categorical assessments will be presented using descriptive statistics as described in section [5.1](#). The descriptive statistics for the bleed related assessments up until week 56 will be presented by treatment arms and ‘Total concizumab’. Furthermore, it will be presented by haemophilia types (HAwI, HBwI).

The evaluation of bleeding episodes at target joints up until 56 weeks will be done between treatment arms and as ‘Total concizumab’.

These descriptive statistics tables will enumerate results for treated bleeds, zero treated bleeds, cause of bleeds (Spontaneous, Traumatic, Surgical), anatomical location of bleeds (Target joints, Joints, Muscular, Skin, Gastrointestinal, Mouth-gums-nose, Urinary system, Central nervous system, Other), classification of bleeds (Mild/moderate, Severe) and location of severe bleeds (Target joints, Joints, Muscular, Skin, Gastrointestinal, Mouth-gums-nose, Urinary system, Central nervous system, Other). The analysis data set use for these descriptive statistics are mentioned in section [5.1](#) of this document.

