Assessment	Number of treated spontaneous and traumatic target joint bleeds	
On demand (arm 1)
 
 
From randomisation (week 0) up until start of concizumab treatment (at least 24 weeks)
 
 
Concizumab (arm 1)
	Count	
Week 56 cut-off is when all patients from arm 2-4 have completed visit 13a assessments or permanently discontinued treatment.
 
Concizumab (arm 1) data available up until week 56 cut-off will be presented.
	5.5.1

		
 
From start of the new concizumab dosing regimen up until week 56 cut-off
 
 
Concizumab (arms 2-4)
 
 
From start of the new concizumab dosing regimen (week 0) up until week 56 cut-off
 
			
Assessment	The number of all spontaneous and traumatic bleeds (treated and untreated)	
On demand (arm 1)
 
 
From randomisation (week 0) up until start of concizumab treatment (at least 24 weeks)
 
 
Concizumab (arm 1)
 
 
From start of the new concizumab dosing regimen up until week 56 cut-off
 
 
Concizumab (arms 2-4)
 
 
From start of the new concizumab dosing regimen (week 0) up until week 56 cut-off
 
	Count	
Week 56 cut-off is when all patients from arm 2-4 have completed visit 13a assessments or permanently discontinued treatment.
 
Concizumab (arm 1) data available up until week 56 cut-off will be presented.
	5.5.1
Assessment	Pre-dose concizumab plasma concentration	
Concizumab (arms 2-4)
 
 
From start of the new concizumab dosing
 
	ng/mL	Summary of pre-dose assessments from start of the new concizumab dosing regimen (week 0) up until week 56.	5.5.2

		regimen (week 0) up until week 56 cut-off			
Assessment	Thrombin peak	At visits where thrombin generation assessments are planned to be measured in the trial up to 56 weeks	nmol/L	Summary of these assessments up until week 56.  From start of the new concizumab dosing regimen (week 0) up until week 56.	5.5.2
Assessment	Free TFPI concentration	At visits where free TFPI assessments are planned to be measured in the trial up to 56 weeks	ng/mL		5.5.2

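### The 56-week SAP classifies arm 1 target joints by the visit 9a list without splitting the arm, so on-demand bleeds would be counted in joints those same bleeds helped to list

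*SAP*

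**What the plan says.** **List of target joints.** SAP section 5.1 gives arms 2-4 the joints registered at baseline. For arm 1 it says: "For arm 1 the target joint evaluation done at visit V9a will be used for assessment at week 56". That sentence does not distinguish the two parts of arm 1.

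**Rows reported.** In SAP Appendix 2 (section 6.2), the treated target-joint bleed count has an on-demand row and a concizumab row for arm 1. The on-demand row runs "From randomisation (week 0) up until start of concizumab treatment (at least 24 weeks". Section 5.5.1 adds: "The evaluation of bleeding episodes at target joints up until 56 weeks will be done between treatment arms".

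**When the visit 9a list is made.** The note to Table 1 in protocol section 5.1 says: "At visit 9a, the patients in arm 1 will start concizumab PPX". In the protocol flowchart the arm 1 re-registration of target joints carries footnote g: "Only applicable for arm 1 patients, who are receiving concizumab at Visit 9a".

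**What makes a target joint.** Protocol section 9.1.4: "A target joint is defined as three or more spontaneous bleeds into a single joint within a consecutive 6-month period". A joint loses the status after two or fewer bleeds in 12 months. At registration: "All current target joints, including number of bleedings during the last 12 months, must be registered".

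**General baseline rule.** The same SAP section does split arm 1 for baseline. For the on-demand part, baseline is the value "recorded before randomisation to the on-demand administration (arm 1". For the concizumab part, it is the last value before the first dose of the new regimen.

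**The concern.** A list used to classify outcome events should be fixed before those events are counted. For arms 2-4 it is. For the arm 1 on-demand row, the only list the SAP names is made when the row closes. A joint that bleeds often during on-demand treatment joins the list because of those bleeds, and they are then counted as target-joint bleeds. A joint that goes quiet can leave the list and take its few bleeds with it. Both effects tend to raise the on-demand rate per patient relative to a prior list, or remove little from it.

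Section 5.5.1 sets the arms side by side, so the inflated comparator row would flatter concizumab in a reported table. There is also a gap: the fallback for a missing visit 9a value is written only for the concizumab part. An arm 1 patient in the full analysis set with no visit 9a evaluation would therefore have no stated list for the on-demand row.

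**Working it through.** The plan states no target-joint rate, so there is no figure of its own to reproduce. The check has three steps.

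**1. Timing**

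| Row | List used (SAP 5.1) | List made | Counting period (Appendix 2) |
|---|---|---|---|
| Arms 2-4, concizumab | Baseline | Before counting | New regimen to week 56 cut-off |
| Arm 1, concizumab | Visit 9a | At start of counting | New regimen to week 56 cut-off |
| Arm 1, on demand | Visit 9a, if read literally | At end of counting | Randomisation to start of concizumab |

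A 24-week period is 24 × 7 = 168 days. Six months is 365.25 / 2 = 182.6 days. The on-demand period therefore fills 168 / 182.6 = 92% of the 6-month look-back at visit 9a. This is window overlap, not effect size.

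**2. Direction, for one joint not listed at screening**

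Assume Poisson spontaneous bleeds at yearly rate λ (not in the documents). With T = 168 / 365.25 = 0.460 years and m = λT:

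- P(N ≥ 3) = 1 − e^(−m)(1 + m + m²/2)
- Expected bleeds counted back as target-joint bleeds = m − e^(−m)(m + m²)

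| λ per year | m | P(N ≥ 3) | Bleeds counted back |
|---|---|---|---|
| 2 | 0.92 | 0.07 | 0.22 |
| 4 | 1.84 | 0.28 | 1.01 |
| 6 | 2.76 | 0.52 | 2.10 |
| 8 | 3.68 | 0.71 | 3.25 |

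With the list made before randomisation, the last column is 0 in every row.

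**3. Size, allowing joints to enter and leave**

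Inputs from the protocol:
- On-demand annual bleeding rate 18 and yearly over-dispersion 13 (section 10.1).
- At least 6 bleeds in 24 weeks or at least 12 in 52 weeks before screening (section 6.4).
- Entry and exit rules of section 9.1.4.

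Assumptions not in the documents:
- Stationary rates and six joints with unequal shares (Dirichlet concentration 1 or 3).
- 60% or 80% of bleeds in joints, and 60% or 80% of those spontaneous.
- 156 weeks of history before screening, followed by 3 weeks of screening.

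Patient rates are gamma with mean 18. Over-dispersion 13 = 1 + 18k gives k = 12/18 = 0.667. Each of the 2 × 2 × 2 = 8 settings simulates 10,000 patients, of whom about 63% meet the bleed criterion. The ratio is on-demand treated bleeds (spontaneous and traumatic) in visit 9a joints divided by those in screening joints.

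| Listing rule | 24 weeks on demand | 36-44 weeks on demand |
|---|---|---|
| Protocol 9.1.4 entry and exit | 1.09 to 1.22 | 1.10 to 1.25 |
| Any qualifying 26-week window in the last 52 weeks | 1.13 to 1.27 | 1.12 to 1.34 |

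The longer periods are included because, under protocol section 5.1, patients randomised to arm 1 before the pause stayed on demand until restart. At 24 weeks under the protocol's rules, 76% to 86% of visit 9a joints were already listed at screening.

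Repeat runs under the protocol's rules gave 1.09 to 1.21 and 1.09 to 1.22 at 24 weeks, and 1.10 to 1.25 and 1.09 to 1.24 at 44 weeks. The 36-week and 52-week look-back results were not repeated. Section 6.4 also admits on-demand patients from the non-interventional study without a bleed count. Dropping the count filter moves the 24-week range to about 1.11 to 1.26.

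**The case against.** The strongest reply is that the sentence was never meant for the on-demand row. Flowchart footnotes g and h tie the later registrations to patients receiving concizumab: visit 9a for arm 1 and visit 2a for arms 2-4. On that view, the two target-joint sentences state one rule, that each arm uses its list from the start of concizumab. The general baseline paragraph already gives a pre-randomisation value for the on-demand part. The SAP also sends main-part analyses to a separate SAP for the primary analysis cut-off, which may settle the list.

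This is plausible as intent, and it is true that the SAP does not expressly apply visit 9a to the on-demand row. It does not cure the text. The baseline rule for week 56 assessments explicitly includes arm 1 on demand and splits it. The more specific target-joint sentence does neither, and it uses the word baseline only for arms 2-4. Appendix 2 lists the on-demand row as an assessment of this SAP under section 5.5.1, which does not defer it elsewhere. If visit 9a was meant only for the concizumab part, the target-joint rule is silent on the on-demand row. Either reading calls for the same added sentence.

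The objection on consequence largely stands. This is one descriptive row in about 17 patients (9 + 8 in protocol Table 2). The assumed shift is small beside the planned contrast for all treated bleeds, 18 against 3 to 5 per year. Total bleeds, all-joint bleeds and the concizumab rows do not change.

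**Conclusion.** The concern holds. If programmed as written, the arm 1 on-demand target-joint rate is biased upward against arms 2-4. Under the protocol's own listing rules the inflation is about 9% to 22% for a 24-week period and 10% to 25% for assumed periods of 36 to 44 weeks. All of these figures depend on the assumed joint shares, spontaneous shares and stationary rates. The direction follows from the target-joint definition and was upward in all eight settings, even with joints allowed to lose status.

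Two limits apply. The wording is ambiguous rather than expressly wrong for the on-demand row, and most visit 9a joints would have been listed at screening anyway. No hypothesis is tested at week 56 and no confirmatory conclusion depends on this row. The SAP for the primary analysis cut-off was not available, so nothing is said about its rule. It remains worth correcting because it changes a reported between-arm figure.

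**What to change.** Split the arm 1 sentence in SAP section 5.1, for example: *In arm 1, on-demand bleeds are classified by the target joints registered at screening (visit 1 or 1a), before randomisation. The visit 9a registration applies only to the concizumab part.* This follows the SAP's existing baseline split. It also gives a list to on-demand patients who have no visit 9a evaluation.

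The cost is one sentence and the matching programming specification. Both protocol flowcharts (section 2 and Appendix 12) already register target joints at screening, so no new data are needed. When making the change, compare it with the rule in the primary-cut-off SAP, so that the same patients and period do not receive two different target-joint rates without explanation.

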| Pre-dose free TFPI concentration                                   | Prior to the concizumab administration at week 24 (after restart)                                                                                                                                                                                                                                                                                                       | ng/mL    |
| Maximum concizumab plasma concentration ( $C_{max}$ )              | From 0 to 24 hours where 0 is time of the concizumab dose at week 24 (after restart)                                                                                                                                                                                                                                                                                    | ng/mL    |
| Area under the concizumab plasma concentration-time curve (AUC)    | From 0 to 24 hours where 0 is time of the concizumab dose at week 24 (after restart)                                                                                                                                                                                                                                                                                    | ng*hr/mL |

aDefined as time of randomisation to on-demand administration or time of start of the new concizumab dosing regimen

bDefined as time of randomisation to on-demand administration or time of start of the initial concizumab dosing regimen (0.25 mg/kg/day).

cDefined as the pause in the concizumab clinical development programme during March to August 2020, while thromboembolic events were investigated

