### Treatment arm 3:

The HAwI and HBwI patients enrolled into the concizumab phase 2 trial (NN7415-4310 (explorer 4)) at time of transfer will be offered enrolment into arm 3 (approximately 25 patients). It

is required that these patients are on concizumab prophylaxis up until enrolment into the trial. These patients will continue concizumab PPX and have a combined visit 1 and 2. All patients from 4310 were transferred to trial 4311 before the pause. Upon restart, patients will receive the new concizumab dosing regimen.

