## **Shared assessments and data transfer from NN7415-4310 (explorer 4) and NN7415-4322 (explorer 6)**

For patients enrolled into this trial from NN7415-4310 (explorer 4) and NN7415-4322 (explorer 6) assessments related to the patient's end of trial and screening visit, respectively, will be baseline assessments for this trial when feasible. The data will automatically be transferred to the database for this trial.

For patients transferring from NN7415-4310 (explorer 4), the following assessments are in scope:

- Laboratory data (End of Trial). See the laboratory manual for details on laboratory sampling for patients who are transferred.
- Details of Haemophilia (screening)
- Haemophilia Treatment and Bleed History (screening)
- ECG (screening)
- PROs (collected at visit 15.1)

For patients transferring from NN7415-4322 (explorer 6), the following assessments are in scope:

- Details of Haemophilia (screening)
- Physical Activity Tracker (screening)

For patients who have previously participated in NN7415-4310 (explorer 4) and NN7415-4322 (explorer 6) following information will be collected in the eCRF:

- Trial ID for previous trial
- Subject number in previous trial

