	
For subjects in arms 2-4 that are only exposed to the initial concizumab dosing regimen, the period begins at the time of start of the initial concizumab PPX regimen.
 
For subjects in arms 2-4 that start on the new concizumab dosing regimen and who have been exposed to the initial dosing regimen, the period consists of two periods with a pause in between. The first period begins at the time of start of the initial concizumab PPX regimen and ends 7 weeks after the treatment was paused while the second period begins at the time of start of the new concizumab PPX regimen.
 
For all cases of arms 2-4 above the periods end at the first occurrence of:
 

• Items 2., 3., 4., 5. or 6. above

On-treatment without data on initial regimen	
The time period where subjects are considered to be affected by on-demand treatment or treatment with the new concizumab dosing regimen.
 
The analysis data set is defined similarly as the ‘on-treatment’ analysis data set with the exception:
 

• Observation time during the initial concizumab PPX regimen is excluded

On-treatment without ancillary therapy a excl. data on initial regimen for subjects exposed to both regimens	
The time period where subjects are treated by either the new concizumab dosing regimen or the initial concizumab dosing regimen (only included if not exposed to the new concizumab dosing regimen) or are treated by on-demand treatment and additionally have not used factor-containing products not related to treatment of a bleed during any of the cases.
 
The analysis data set is defined similarly as the ‘on-treatment’ analysis data set with the exception:
 

• Periods where factor containing products not related to treatment of a bleed have been used are excluded

• For subjects in arms 2-4 that start on the new concizumab dosing regimen and who have been exposed to the initial dosing regimen, the data on the initial concizumab PPX regimen are excluded

a Ancillary therapy is defined as use of factor-containing products not related to treatment of a bleed.

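### The week-56 baseline rule sets no earliest date for restarters, so its fallback cannot operate and it can select a value taken on the initial regimen

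*SAP*

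**What the plan says.** SAP 5.1 (General considerations) defines the week-56 baseline for arms 2–4 as "the latest non-missing measurement recorded before the time of the first administration of concizumab with the new dosing regimen". The next sentence gives two triggers for a fallback: "If this measurement is missing for arms 2-4 or a subject from arms 2-4 chooses not to restart on concizumab". It then names the replacement: "then the baseline obtained prior to the initial dosing regimen will be used (if available"). For arm 1 on concizumab, a parallel sentence names visit 9a and allows the latest earlier measurement instead.

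SAP section 4 describes restarters in arms 2–4: "the period consists of two periods with a pause in between". It adds: "The first period begins at the time of start of the initial concizumab PPX regimen and ends 7 weeks after the treatment was paused". SAP Table 1 assigns PK, PD and non-event safety to a data set that leaves out observation time on the initial regimen. Nothing ties that exclusion to the choice of baseline. Protocol 4.3.2.2 (footnote b) gives the initial regimen as 0.25 mg/kg/day.

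Protocol 10.3.2.1 states a different baseline rule for the SF-36 analyses: the value just before the restart and, failing that, the value before the initial randomisation.

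For arm 3, protocol 5.1 says it is "required that these patients are on concizumab prophylaxis up until enrolment into the trial". The protocol's part on shared assessments and data transfer says that, for patients coming from the phase 2 trial and the non-interventional study, "assessments related to the patient's end of trial and screening visit, respectively, will be baseline assessments for this trial when feasible".

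**The concern.** Read together, the two SAP sentences defeat each other. The first has no lower time limit and does not exclude the initial-regimen period, so every value before the initial regimen already satisfies it. The second is written as a safeguard that takes the patient back to before the initial regimen, but for a restarter it has nothing left to find.

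What is at stake is the reference point for change from baseline in the safety laboratory parameters, weight, vital signs and physical examination (SAP Appendix 2). The laboratory set includes D-dimer, prothrombin fragments 1+2 and fibrinogen (protocol Table 18), which bear on the thromboembolic risk that caused the pause. If a marker moves on concizumab, a reference value taken on concizumab will tend to understate the change in that patient.

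**Working it through.** The documents give no figure to reproduce. The check is on the logic of the rule.

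**1. Set relation.** Let A be the values before the first dose of the initial regimen and B the values before the first dose of the new regimen. For a restarter the initial regimen precedes the new one, so A is contained in B. The first rule fails only if B has no non-missing value. Then A has none either, and the fallback returns nothing.

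**2. Enumeration.** Divide a restarter's record for one parameter into four slots: before the initial regimen, on the initial regimen, in the pause, and visit 2a pre-dose. Each is present or missing, giving 2⁴ = 16 patterns. The fallback supplies a value in 0 of 16. If no pause visits took place there are 2³ = 8 patterns, and it supplies a value in 0 of 8.

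The patterns with visit 2a missing compare as follows. The SF-36-style rule is visit 2a, else before the initial regimen.

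| Value selected | SAP rule, pause visits possible (8) | SF-36-style rule (8) | SAP rule, no pause visits (4) | SF-36-style rule (4) |
|---|---|---|---|---|
| Pause | 4 | 0 | – | – |
| On initial regimen | 2 | 0 | 2 | 0 |
| Before initial regimen | 1 | 4 | 1 | 2 |
| None | 1 | 4 | 1 | 2 |

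These count patterns, not patients. In the one pattern where the SAP rule gives the value before the initial regimen, it does so through the first sentence, not the fallback. When values exist both before and on the initial regimen and there is no pause value, the SAP rule takes the on-drug value and the SF-36-style rule takes the earlier one.

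**3. Can the on-drug case arise?** Restarters in arms 2–4 re-enter directly at visit 2a (protocol Table 1). Only new patients have visit 1a, so restarters have no scheduled screening sample between the pause and visit 2a. The pre-pause schedule kept in protocol Appendix 12 has haematology, biochemistry, coagulation parameters and vital signs at visits during treatment. The next candidate after a missing visit 2a value is therefore a pause value, if there is one, and otherwise a value on the initial regimen.

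**4. Is a pause value off drug?** Not always. The SAP's on-treatment period for event-type safety runs to 7 weeks after the pause. The programme pause lasted from March to August 2020 (protocol 4.3.2.2, footnote c). Even from 31 March to 1 August that is 123 days, or 123/7 = 17.6 weeks, so a pause value could fall on either side of the 7-week limit.

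**5. Who is not affected.** New patients have no initial-regimen period. Earlier values in arm 1 were taken on demand, before any concizumab. For patients who do not restart, the fallback does work.

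**The case against.** The strongest reply is that this is a slip of wording. The arm 1 sentence names visit 9a, so the missing measurement in arms 2–4 is probably meant to be the visit 2a value. On that reading the fallback works and matches protocol 10.3.2.1. Derivation details are also deferred to the analysis data reviewer's guide, which is not available here. The likely intention stands, but the text does not say it. A programmer following the text would take the latest value, and the guide should not have to override the SAP.

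Several stronger readings are tempting, and the documents do not support them:

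- **That the rule always picks an on-drug value when visit 2a is missing.** Protocol 8.1 asks patients off trial product to keep attending visits. A pause value would be chosen first and may be off drug.
- **That a substantial share of baselines is affected.** No missing rate is given. Coagulation, haematology and biochemistry have priorities 1 to 3 when adolescent blood volume is limited (protocol Table 20), and all are scheduled at visit 2a.
- **That the affected changes would be about zero.** The reference would be on 0.25 mg/kg/day, while follow-up starts at 0.20 mg/kg with possible adjustment.
- **That every arm 3 fallback baseline is currently on drug.** As the text stands, an arm 3 restarter never reaches the fallback. An arm 3 patient who does not restart has no new-regimen time in the non-event safety data set. The arm 3 difficulty appears only once the rule is repaired.
- **That thromboembolic event counts or the primary result could change.** Event counts do not use a baseline, and SAP section 1 limits the week-56 analyses to description.

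**Conclusion.** The point holds in a limited form. The stated fallback is unreachable for restarters; this follows from the wording alone and needs no assumption about the data. The rule can also select a value taken on the initial regimen, or within the seven weeks after the pause that the SAP still counts as on-treatment for events. That second part requires three conditions: the visit 2a value is missing, an on-treatment pre-pause value exists, and no later pause value exists (for a value within the seven weeks, none after it).

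The effect is confined to descriptive change-from-baseline summaries in restarters without a visit 2a value for the parameter concerned. Their number is not given; given the scheduling and sampling priority at visit 2a it is probably small. No confirmatory result changes. It is still worth correcting: the rule contradicts itself, departs without explanation from the protocol's SF-36 rule, and sits uneasily with the SAP's exclusion of initial-regimen time for the same class of assessments.

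**What to change.** In SAP 5.1 and the matching derivation:

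- For restarters in arms 2–4, define baseline as the visit 2a pre-dose value and, if that is missing, the last value before the first dose of the initial regimen.
- State that values from the first initial-regimen dose until 7 weeks after the pause are not eligible.
- State whether later pause values may be used and, if so, where they rank.
- For arm 3, note that the value before the initial regimen was itself taken on phase 2 concizumab. The laboratory data listed for transfer are end-of-trial data only, so no concizumab-free laboratory value is named as a substitute. If visit 2a is missing, flag these patients or show observed values only.

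The cost is a short text change and one derivation. A few patients may drop out of the change tables: with visit 2a missing and no pause visits, the revised rule gives no baseline in 2 of 4 patterns, against 1 of 4 under the present text.
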